#### 8.1.2 Definition of Serious Adverse Events (SAE)

#### **Serious Adverse Event**

Adverse events are classified as serious or non-serious. A serious adverse event is any AE that is:

- fatal
- life-threatening
- requires or prolongs hospital stay
- · results in persistent or significant disability or incapacity
- a congenital anomaly or birth defect
- an important medical event

Important medical events are those that may not be immediately life threatening, but are clearly of major clinical significance. They may jeopardize the subject, and may require intervention to prevent one of the other serious outcomes noted above. For example, drug overdose or abuse, a seizure that did not result in in-patient hospitalization, or intensive treatment of bronchospasm in an emergency department would typically be considered serious.

All adverse events that do not meet any of the criteria for serious should be regarded as non-serious adverse events.

Version Date: September 27, 2019

#### 8.1.3 Definition of Unanticipated Problems (UP)

#### **Unanticipated Problems Involving Risk to Subjects or Others**

Any incident, experience, or outcome that meets all of the following criteria:

• Unexpected in nature, severity, or frequency (i.e. not described in study-related documents such as the IRB-approved protocol or consent form, the investigators brochure, etc.)

- Related or possibly related to participation in the research (i.e. possibly related means there is a
  reasonable possibility that the incident experience, or outcome may have been caused by the
  procedures involved in the research)
- Suggests that the research places subjects or others at greater risk of harm (including physical, psychological, economic, or social harm).

#### 8.2 Classification of an Adverse Event

#### 8.2.1 Severity of Event

For AEs not included in the protocol defined grading system, the following guidelines will be used to describe severity.

- Mild Events require minimal or no treatment and do not interfere with the participant's daily activities.
- Moderate Events result in a low level of inconvenience or concern with the therapeutic measures. Moderate events may cause some interference with functioning.
- Severe Events interrupt a participant's usual daily activity and may require systemic drug therapy or other treatment. Severe events are usually potentially life-threatening or incapacitating.

#### 8.2.2 Relationship to Study Intervention

The clinician's assessment of an AE's relationship to study intervention is part of the documentation process, but it is not a factor in determining what is or is not reported in the study. If there is any doubt as to whether a clinical observation is an AE, the event should be reported. All AEs must have their relationship to study intervention assessed. In a clinical trial, the study intervention must always be suspect. To help assess, the following guidelines are used.

- Related The AE is known to occur with the study intervention, there is a reasonable possibility that
  the study intervention caused the AE, or there is a temporal relationship between the study
  intervention and event. Reasonable possibility means that there is evidence to suggest a causal
  relationship between the study intervention and the AE.
- Not Related There is not a reasonable possibility that the administration of the study intervention
  caused the event, there is no temporal relationship between the study intervention and event onset, or
  an alternate etiology has been established.

#### 8.2.3 Expectedness

[name] will be responsible for determining whether an AE is expected or unexpected. An AE will be considered unexpected if the nature, severity, or frequency of the event is not consistent with the risk information previously described for the study intervention. As this study is minimal risk, no adverse events are expected.

#### 9.3 Time Period and Frequency for Event Assessment and Follow-Up

The occurrence of an AE or SAE may come to the attention of study personnel during study visits and interviews of a study participant presenting for medical care, or upon review by a study monitor. All AEs including local and systemic reactions not meeting the criteria for SAEs will be captured on the appropriate RF. Information to be collected includes event description, time of onset, clinician's assessment of severity, relationship to study intervention (assessed only by those with the training and authority to make a diagnosis),

Version Date: September 27, 2019

and time of resolution/stabilization of the event. All AEs occurring while on study must be documented appropriately regardless of relationship. All AEs will be followed to adequate resolution.

Any medical condition that is present at the time that the participant is screened will be considered as baseline and not reported as an AE. However, if the study participant's condition deteriorates at any time during the study, it will be recorded as an AE. UPs will be recorded in the data collection system throughout the study.

Changes in the severity of an AE will be documented to allow an assessment of the duration of the event at each level of severity to be performed. AEs characterized as intermittent require documentation of onset and duration of each episode.

The PI will record all reportable events with start dates occurring any time after informed consent is obtained until 7 (for non-serious AEs) or 30 days (for SAEs) after the last day of study participation. At each study visit, the investigator will inquire about the occurrence of AE/SAEs since the last visit. Events will be followed for outcome information until resolution or stabilization.

All unresolved adverse events should be followed by the investigator until the events are resolved, the subject is lost to follow-up, or the adverse event is otherwise explained. At the last scheduled visit, the investigator should instruct each subject to report any subsequent event(s) that the subject, or the subject's personal physician, believes might reasonably be related to participation in this study. The investigator should notify the study sponsor of any death or adverse event occurring at any time after a subject has discontinued or terminated study participation that may reasonably be related to this study.

#### 9.4 Reporting Procedures - Notifying the IRB

#### 9.4.1 Adverse Event Reporting

AEs are not expected due to participation in this minimal risk study. However, AE forms will be completed at each of the study assessments as well as any AEs reported during the weekly intervention sessions.

Study participants will be encouraged to contact study staff immediately should any AEs occur during study participation. Periodic adverse event reporting will include any AE that occurs while a participant is on the research protocol, regardless of whether it is considered related to study participation.

The PI will submit as part of annual progress reports to the IRB a summary of monitoring that took place; cumulative adverse event data; assessments that were performed to evaluate external factors or relevant information that may have an impact on the safety of study participants or ethics of the research study; outcomes of procedural reviews conducted to ensure participant privacy and confidentiality; and final conclusions regarding changes to the anticipated risk-to-benefit ratio of study participants and recommendations related to continuing, changing, or terminating the study.

#### 9.4.2 Serious Adverse Event Reporting

SAEs are not expected due to participation in this minimal risk study. The procedure for AE reporting will be followed for SAEs. In addition, if a serious adverse event occurs, it will be reported in a timely fashion after adjudication: All SAE reports will be made to the IRB within 5 working days; any participant deaths will be reported to the NINR Program Officer within 24 hours of realization, and all other serious adverse events will be reported to NINR within 72 hours of realization.

#### 9.4.3 Unanticipated Problem Reporting

Incidents or events that meet the OHRP criteria for UPs require the creation and completion of an UP report form. It is the site investigator's responsibility to report UPs to their IRB and to the DCC/study sponsor. The UP report will include the following information:

- Protocol identifying information: protocol title and number, Pl's name, and the IRB project number;
- A detailed description of the event, incident, experience, oroutcome;
- An explanation of the basis for determining that the event, incident, experience, or outcome represents an UP;

Version Date: September 27, 2019

• A description of any changes to the protocol or other corrective actions that have been taken or are proposed in response to the UP.

To satisfy the requirement for prompt reporting, UPs will be reported using the following timeline:

 UPs that are SAEs will be reported to the IRB and to the study sponsor within the timeframe described in 8.4.2

- Any other UP will be reported to the IRB and to the study sponsor within the timeframe described in 8.4.1 for AEs.
- All UPs should be reported to appropriate institutional officials (as required by an institution's written
  reporting procedures), the supporting agency head (or designee), and OHRP within the Time frame
  described for AEs or SAEs, as appropriate, after the IRB's receipt of the report of the UP from the
  investigator.

### 9.4.4 Reporting of Pregnancy

Pregnant or breastfeeding participants will not be able participate in the study because pregnancy and lactation can disrupt habitual sleep patterns, and hormonal changes during pregnancy increase insulin resistance and may confound MetS. If participants become pregnant during the course of the study, their data will not be used in the analyses.

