#### 4.2 Exclusion Criteria

An individual who meets any of the following criteria will be excluded from participation in this study:

- 1. Pregnancy/lactation (self-reported). Pregnancy and lactation can disrupt habitual sleep patterns, and hormonal changes during pregnancy increase insulin resistance and may confound MetS.
- Current chemotherapy treatments (self-reported). Current chemotherapy treatments may contribute to fatigue and sleep disturbances.
- Alcohol abuse will be assessed with the Alcohol Use Disorders Identification Test (a measure that has demonstrated good reliability and validity). Alcohol abuse/dependence may contribute to sleep disturbances and limit the participant's ability to take part in sleep interventions. Individuals with scores > 15 (men) or > 13 (women) will be excluded.
- 4. Night shift or shift work (previous 2 months), trans-meridian travel (previous 4 weeks), or planned shift work or trans-meridian travel during intervention period (self-reported). These will be to ensure that sleep estimates from baseline represent participants' habitual sleep and to ensure adherence with the sleep intervention.
- 5. Moderate-severe or severe depression will be assessed with the Patient Health Questionnaire (PHQ-9). The PHQ-9 is reliable and has been shown to have construct and criterion validity (Kroenke et al, 2001). Using professional interviews as the criterion standard, a PHQ-9 score of 10 had a sensitivity of 88% and a specificity of 88% for detecting major depression. It has been validated in clinical populations and been used in a large number of cardiovascular studies. Moderate-severe depression or severe depression may contribute to sleep disturbances and interfere with the participant's ability to adhere to the sleep interventions. Therefore, individuals with scores ≥ 15 will be excluded.
- 6. Chronic use of sleep-promoting medications (self-reported) defined as taking a sleep-promoting medication ≥ 3 nights per week. These may interfere with sleep patterns and limit the participant's ability to take part in the sleep interventions.
- 7. Habitual napping, defined as 2 naps per day or > 90 minutes of napping on 3 or more days of the week will be assessed during baseline with accelerometry. This will be to ensure adherence with the sleep intervention.

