#### 4.5.1 Reasons for Withdrawal or Termination

Participants are free to withdraw from participation in the study at any time upon request. An investigator may terminate participation in the study if:

- Any clinical adverse event (AE), laboratory abnormality, or other medical condition or situation occurs such that continued participation in the study would not be in the best interest of the participant
- The participant meets an exclusion criterion (either newly developed or not previously recognized) that precludes further study participation.
- The participant does not respond to phone calls/emails for 4 weeks during the intervention.

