#### 4.5.2 Handling of Participant Withdrawals or Termination

Participants will be considered withdrawn if they cannot be contacted for 4 weeks during the intervention using all of the contact information collected. No further efforts will be made to contact the participant and that participant will be considered lost to follow-up. Abrupt termination of participation in the study intervention poses no safety risk to participants. As this study is minimal risk, efforts will not be made to collect safety and efficacy data after withdrawal.

Any data collected before withdrawal from the study will be retained for analysis, and no new data will be collected. If the participant requests that data be destroyed, all paper records will be shredded, and any data already processed into computer files will be removed. However, if results based on the participant's data have been submitted for publication or presentation before the request is made, the results cannot be removed from the publication or presentation.

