## 12.3 Analysis Datasets

The analysis dataset will include all participant (e.g., intent to treat).

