### 12.4.2 Analysis of the Primary Efficacy Endpoint(s)

For Aim 1: Acceptability will be based on the pre- and post-intervention acceptability survey measurements. The acceptability survey is an ordinal scale with higher scores indicating greater acceptability. Results will be reported as a categorical outcome indicating the count and percentage of participants rating SASI at the pre-intervention assessment as well as the post intervention assessment as acceptable (total scores greater than or equal to 21), neutral (total score equal to 21), and unacceptable (total scores less than 21).

Feasibility will be based on recruitment, retention, and study protocol adherence. Recruitment will be measured as the number and percentage of participants screened and their determination as eligible or ineligible based on inclusion/exclusion criteria. Results will be reported as a recruitment rate indicating the count and percentage of participants eligible and ineligible. Attrition rates will be reported as the number

and percentage of participants who withdraw from the study. Attrition rates >20% will suggest lack of feasibility. Recruitment and attrition rates will also be examined for differences in specific subgroups. Study protocol feasibility will be indicated by percentage of participants providing at least 4 work day sleep diaries per week for greater than or equal to 80% of the intervention period.

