### 12.4.5 Adherence and Retention Analyses

Adherence and retention are the primary endpoints for this pilot study.

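### Section 9.4.4 drops the data of participants who become pregnant, which conflicts with Sections 12.3 and 4.5.2 and rests on a reason that does not reach the primary endpoints

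*Combined protocol and SAP*

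**What the plan says.** Section 9.4.4 (Reporting of Pregnancy) states: "If participants become pregnant during the course of the study, their data will not be used in the analyses". The reason in the same paragraph is that pregnancy and lactation can disturb habitual sleep and that hormonal changes raise insulin resistance and may confound metabolic syndrome.

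Two other sections set the analysis population without a pregnancy exception. Section 12.3 says: "The analysis dataset will include all participant (e.g., intent to treat". Section 4.5.2 says: "Any data collected before withdrawal from the study will be retained for analysis, and no new data will be collected". The only removal that Section 4.5.2 describes is at the participant's own request. Section 9.4.4 refers to neither section.

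Pregnancy is the first exclusion criterion in Section 4.2, "Pregnancy/lactation (self-reported", and Section 4.5.1 lets the investigator end participation if "The participant meets an exclusion criterion (either newly developed or not previously recognized) that precludes further study participation".

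On the endpoints, Section 12.4.5 says "Adherence and retention are the primary endpoints for this pilot study", and Section 3.2.1 also makes acceptability primary. Section 12.4.2 gives the attrition marker: "Attrition rates >20% will suggest lack of feasibility".

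**The concern.** Section 9.4.4 excludes people from the analysis because of something that happens after enrolment. An analyst faced with a pregnancy on study has one section saying to leave her data out and two saying to keep them, with nothing to rank the three. The same woman can be a withdrawal whose earlier data are kept (Sections 4.5.1 and 4.5.2) and a person whose data are not used at all (Section 9.4.4).

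The stated reason may justify caution with sleep, symptom and metabolic measures. It does not explain leaving someone out of the counts of who stayed, who kept the diary and who found the intervention acceptable. If the conflict is settled only after a case has arisen, the choice is made with the data in view.

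**Working it through.** **Which data the stated reason covers**

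- Attrition, diary adherence and acceptability (primary): the reason concerns sleep and metabolic confounding, so it does not apply.
- Pre-post sleep, fatigue, behaviour and symptom measures (secondary): the reason is plausible for data after conception, but not for baseline data from before it.
- Recruitment: Section 12.4.2 counts people as eligible or ineligible at screening. A later pregnancy does not naturally undo that count.

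**Planned numbers**

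Inputs from Sections 4 and 12.5: 220 screened, 65% found ineligible, 20% lost, final N = 60.

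- Entering the intervention: 220 × (1 − 0.65) = 77.
- Completing: 77 × (1 − 0.20) = 61.6, against the stated 60.
- Backwards: 60 / 0.80 = 75 entering, and 75 / 0.35 = 214.3, so 215 screened, against the stated 220.

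The plan's figures therefore reproduce to within 3%, with 75 to 77 entering. Expected attrition, 20%, equals the marker in Section 12.4.2.

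**Effect of deleting one participant on attrition**

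With w withdrawals among n participants, the rate is w/n. Deleting a withdrawal gives (w − 1)/(n − 1). Deleting a completer gives w/(n − 1). The marker is passed only when the rate is strictly above 20%.

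| n | w | All kept | One withdrawal deleted | One completer deleted |
|---|---|---|---|---|
| 77 | 15 | 19.5% | 14/76 = 18.4% | 15/76 = 19.7% |
| 77 | 16 | 20.8% | 15/76 = 19.7% (crosses) | 16/76 = 21.1% |
| 77 | 17 | 22.1% | 16/76 = 21.1% | 17/76 = 22.4% |
| 75 | 15 | 20.0% | 14/74 = 18.9% | 15/74 = 20.3% (crosses) |

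For every n from 58 to 80 there is exactly one withdrawal count at which a single deletion crosses the marker. When n is a multiple of 5, the deletion must be of a completer, and attrition moves above the marker. Otherwise it must be of a withdrawal, and attrition moves to the marker or below it.

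Section 3.2.1 speaks of enrolling 60. With that denominator, 12/60 = 20.0% becomes 12/59 = 20.3% when a completer is deleted.

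**How often the count would sit there**

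Assume binomial attrition at the planned 20%. The chance of exactly 16 of 77 is 0.110, and of exactly 15 of 75 is 0.114. If true attrition is 15% or 25%, these become 0.044 or 0.076, and 0.058 or 0.068. Each must then be multiplied by the chance of a pregnancy in the right kind of participant, which the documents do not give. If that chance is assumed to be 1% to 10%, the product at n = 77 and 20% attrition is 0.110 × 0.01 = 0.1% to 0.110 × 0.10 = 1.1%.

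**The case against.** The best defence is that Section 9.4.4 is a specific, prespecified exception to a one-sentence general rule. Section 12.1 says that the statistical section is only an overview, with a formal SAP to follow. The reason given also suggests that the author had sleep and metabolic outcomes in mind, and Section 12.4.2 defines attrition by who withdraws, so a pregnant participant who is withdrawn might still be tallied there. Termination under Section 4.5.1 is discretionary as well.

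Part of this stands. The narrow reading is possible, and full deletion from every endpoint is not a certainty. But the text does not limit itself, and Sections 12.3 and 4.5.2 leave no room for an exception, so the conflict remains.

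A reader might go further and infer that a single pregnancy would overturn the feasibility conclusion, or that the rule makes the study look more feasible. The documents do not support either inference. A crossing needs one exact withdrawal count, it can go in both directions, and the 20% figure is a descriptive indication beside the recruitment, adherence and acceptability results. No test or binding decision is attached to it. Nor do the documents support saying that recruitment data are lost.

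**Conclusion.** The conflict is real and can be read directly from the text: Section 9.4.4 cannot be applied as written together with Sections 12.3 and 4.5.2, and its reason does not reach the primary attrition, adherence and acceptability endpoints. This is a clash between stated rules, not just missing detail.

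The likely effect on results is small. That judgement rests on an assumption that few pregnancies will occur among men and women aged 35 to 60. The crossing of the 20% marker shows only that the choice of rule can matter: it is rare, and under the assumed ranges above its chance is about 1% or less. The point is a minor correction, worth making because it is easy and is best settled before a case arises.

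**What to change.** Amend Section 9.4.4, and carry the same rule into the SAP, as follows:

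- All enrolled participants stay in the attrition, diary-adherence and acceptability counts. Pregnancy is listed as the reason for any withdrawal it leads to.
- Data collected from a participant who becomes pregnant stay in the intent-to-treat dataset, in line with Sections 12.3 and 4.5.2.
- A prespecified sensitivity analysis of the secondary pre-post outcomes (sleep, fatigue, behaviours) omits participants who became pregnant.

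The sensitivity analysis should omit the whole participant. A cut-off at the date pregnancy is reported would leave observations from between conception and the report in the analysis. For a withdrawn participant there would be nothing after that date to remove, since Sections 4.5.2 and 7.5 end data collection at withdrawal.

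The cost is a short text change, with no effect on sample size, procedures or clinical management. There is one small downside: the main secondary analysis may contain a few observations affected by pregnancy, which the sensitivity analysis would show.

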#### 10.5 Reporting Procedures – Notifying the Study Sponsor

The study clinician will complete a SAE Form within the following timelines:

- All deaths and immediately life-threatening events, whether related or unrelated, will be recorded on the SAE Form and submitted to the DCC/study sponsor within 24 hours of site awareness. See Section 1, Key Roles for contact information.
- Other SAEs regardless of relationship will be submitted to the DCC/study sponsor within 72 hours of site awareness.

All SAEs will be followed until satisfactory resolution or until the site investigator deems the event to be chronic or the adherence to be stable. Other supporting documentation of the event may be requested by the DCC/study sponsor and should be provided as soon as possible.

As a follow-up to the initial report, within the following 48 hours of awareness of the event, the investigator shall provide further information, as applicable, on the unanticipated event or the unanticipated problem in the form of a written narrative. This should include a copy of the completed Unanticipated Problem form, and any other diagnostic information that will assist the understanding of the event. Significant new information on ongoing unanticipated adverse effects shall be provided promptly to the study sponsor.

